11. TREATMENTS

11.1 Patient pathway and Schedule of visits

Please refer to Appendices 3 - 5 for a breakdown of the patient pathway and Schedule of Visits (Stage 1 and 2).

11.2 Dexamethasone (standard care – non IMP)

Dexamethasone is also prescribed to patients in the PROSSPER trial but is the non IMP and will be supplied from hospital stock.

Dexamethasone will be prescribed as standard of care taken orally in the morning within 30 minutes of finishing breakfast.

At time of randomisation, patients must have been on 4mg-12mg of dexamethasone for at \geq 48 hours.

Stage 1: Day 1 – 10 (Please refer to Appendix No.6 - Doses Stage 1)

Pharmacokinetic sampling days are Day 1 and one other day between Days 5 and 10. This day will be decided by the clinical team and patient

On Day 1, patients will take 8mg dexamethasone in the morning.

On Days 2-10, patients will take dexamethasone in the morning as clinically indicated, except on the second pharmacokinetic sampling day when the dose of dexamethasone will be 8mg.

Stage 2: Day 1 – 22 (Please refer to Appendix No.7 - Doses Stage 2)

On Day 1, patients will take 8mg dexamethasone in the morning.

From Day 3-14, if clinically appropriate, the dexamethasone dose will be reduced by 2mg/day on alternate days (see Appendix 6 [Drug Table Stage 1] and Appendix 7 [Drug Table Stage 2]) and can be discontinued if indicated.

Should symptoms of raised intracranial pressure recur, the dose of dexamethasone will be increased by 4mg (i.e. to 2mg above the dose at which the patient's symptoms had been controlled).

Once the dose has been re-escalated, and after Day 14, subsequent dose adjustments will be at the clinician's discretion.

11.3 Micronised progesterone/placebo (IMP)

Micronised progesterone/placebo is the trial IMP and will be provided by the manufacturer as 200mg capsules. Progesterone/placebo should be taken orally within 30 minutes of finishing a meal.

Stage 1: Day 1-10 (Please refer to Appendix No.6 - Doses Stage 1)

On Day 1, patients will take 200mg micronized progesterone in the morning after breakfast (08.00 - 10.00).

A further dose of 600mg of micronized progesterone will be taken on another day between Days 5-10. This day will be decided by the clinical team and patient.

Stage 2: Day 1-22 (Please refer to Appendix No.7 - Doses Stage 2)

The Stage 2, Day 1 starting dose of micronized progesterone/placebo will be determined by the pharmacokinetic results of Stage 1.

In Stage 2, patients will also take progesterone/placebo at 08.00 - 10.00 (breakfast), 12.00 – 14.00 (lunch) and 17.00 – 19.00 (dinner). Patients will record the time each meal is completed and micronised progesterone (or placebo in Stage 2) taken.

Patients will continue on this dose to Day 14 unless they do not tolerate this initial micronised progesterone/placebo dose due to side-effects. In that case, the dose of micronized progesterone/placebo will be reduced by 200mg; if that reduced dose is not tolerated, it will be reduced by a further 200mg. If the second reduced dose is not tolerable, the patient will be withdrawn from the study. For example, if the initial dose of micronized progesterone/placebo was 600mg t.d.s (three times a day) i.e. 1800 mg/day, the first dose reduction would be 400mg t.d.s, i.e. 1200mg/day in total and further dose reduction would be 200mg t.d.s. i.e. 600mg/day in total.

See Appendix 6 [Drug Table Stage 1] and Appendix 7 [Drug Table Stage 2]) for Drug tables.

Day 15-22 involves trials procedures but not micronized progesterone/placebo.

11.4 Missed or vomited doses

If a patient vomits within an hour of taking a dose, the Research Team should email the PROSSPER team ([contact]) to seek advice. The PROSSPER team may advise that an additional dose (IMP or Dexamethasone) should be taken. If a patient misses a dose, an additional dose (IMP or Dexamethasone) should be taken late unless omission not noticed until next administration of that drug.

11.5 Concomitant Therapy

Patients should receive concomitant medications as clinically indicated. These will be recorded in the CRF. Patients requiring to start hormone replacement therapy or coumarin anticoagulants should be withdrawn from the study.

11.6 IMP storage and accountability

More detail on IMP (micronized progesterone/placebo) storage and accountability are contained in the PROSSPER Pharmacy Manual.

11.6.1 Storage

All IMP must be kept in a secure place under appropriate storage conditions 15°C - 25°C. A description of the appropriate storage and shipment conditions for the study IMP are specified on the IMP labels. IMP must be kept out of the reach and sight of children.

11.6.2 Accountability and IMP compliance

The investigator or a delegated individual (e.g. pharmacist) must ensure that the IMP is stored and dispensed in accordance with hospital standard operating procedures and applicable regulatory requirements.

The medication provided for this study is for use only as directed in the protocol. Patients must be asked to bring all their trial medication (including any unused) every time they attend the clinic for the purposes of treatment compliance assessment and drug accountability.

Drug distribution and accountability logs will be provided to the site in a pharmacy pack. It is the investigator's responsibility to establish a system for handling the IMP to ensure that:

- Deliveries of IMP are correctly received by a responsible person (e.g., pharmacist or suitable pharmacy designee) and are handled and stored correctly and safely
- IMP are dispensed only in accordance with the protocol
- Participants return any unused IMP to the PI/Research nurse at the end of the trial
- A dispensing record (which will include the identification of the participant to whom the IMP was dispensed, the date of dispensing, the quantity of IMP dispensed, the date and quantity of any unused IMP returned to the pharmacy, delays and reasons for delays) is accurately maintained. Any discrepancies must be accounted for on the appropriate form.

In the case that any IMP is damaged, please contact SCTRU for reconciliation and replacement.

At the termination of the study or at the request of the sponsor, all unused drugs will be accounted for and destroyed locally at the study sites. Certificates of delivery and destruction or return must be signed and copies retained in the Investigator Site File.

11.7 IMP Supplies and Labelling

More detail on IMP Supplies and Labelling are contained in the PROSSPER Pharmacy Manual.

11.7.1 Supply

The IMP (micronised progesterone/placebo) is supplied free of charge by Besins Healthcare (UK) in capsules contained in blister packs. Besins Healthcare (UK) Ltd will supply both progesterone and placebo (placebo will be coated with sunflower oil so will taste and look the same as progesterone).

11.7.2 Labelling

All IMP supplied by Besins Healthcare (UK) Ltd will be re-packaged and labelled according to Annex 13 of the 'Good Manufacturing Practice'. The drugs will be re-packaged, labelled, QP released and distributed by Mawdsleys to sites.

11.8 Assessment of efficacy

No formal comparison of efficacy will be made.

12. PHARMACOVIGILANCE

12.1 Definitions

Adverse Event (AE): An adverse event is any untoward medical occurrence in a patient which does not necessarily have a causal relationship with the IMP or procedures. An adverse event can therefore be any unfavourable and unintended sign (including an abnormal laboratory finding), symptom, or disease temporally associated with a treatment or procedure, whether or not considered related.

Adverse Reaction (AR): All noxious and unintended responses related to a IMP or procedure should be considered adverse drug reactions.

Serious Adverse Event (SAE): Any untoward medical occurrence in a patient that

- a) Results in death
- b) Is life-threatening
- c) Requires hospitalisation or prolongation of existing hospitalisation
- d) Results in persistent or significant disability or incapacity
- e) Consists of a congenital anomaly or birth defect
- f) Is otherwise considered to be medically significant by the investigator

The term “life-threatening” refers to an event in which the patient was at risk of death at the time of the event; it does not refer to an event which hypothetically might have caused death if it were more severe.

Hospitalisations planned prior to enrolment in the trial, scheduled by the trial protocol, or for social reasons, will not be considered as SAEs unless the hospitalisation has to be prolonged as a result of the AE. Treatment in an emergency room of less than 24 hours or on an out-patient basis that does not meet any other serious criteria should not be considered as an SAE.

Suspected Unexpected Serious Adverse Reaction (SUSAR): A suspected unexpected serious adverse reaction is an adverse reaction that is classified as serious and it is thought to be caused by a IMP or procedure. Expected events are detailed within the Summary of Product Characteristics (SmPC). The nature, severity or outcome of this adverse reaction must not be consistent with SmPC for the treatment for it to be reported as a SUSAR.

12.2 Recording and reporting of Adverse Events

All Adverse Events will be recorded in the Case Report Form and graded according to Common Terminology Criteria for Adverse Events (CTCAE) version 5. The Investigator, or delegated co-investigators, will assess each event for relatedness. Any AE considered related becomes an AR.

All adverse events that occur after the signing of written informed consent and within 30 days after the final IMP will be recorded on the appropriate eCRF page. In addition, any events occurring more than 30 days after final IMP that are deemed to be related to the IMP should be notified to PHS by emailing [contact].

12.3 Recording and reporting of Serious Adverse Events

All serious adverse events that occur after the signing of written informed consent and within 30 days after the final IMP will be recorded on the SAE report form on the trial eCRF. The CTCAE grading will also be captured. The Investigator, or delegated co-investigators, will assess each event for relatedness. Any SAE considered related becomes a SAR.

In addition, any events occurring more than 30 days after final IMP that are deemed to be related to the IMP should be notified to PHS by emailing [contact].

The SAE case report form must be completed on the Trial eCRF and signed by the Principal Investigator, or delegated co-investigator of the centre involved, within 24 hours of the site team becoming aware of the event.

All initial SAE reports should contain the following minimum information:

- Reporter information
- At least one subject identifier (trial number/patient initials)
- Event term
- Assessment of relatedness
- Suspect drug or procedure
- Serious criteria

Sites must email [contact] to notify PHS that an SAE has been reported.

All SAEs will be forwarded to the CI by PHS for assessment of relatedness, and expectedness against the SmPC. Any SAE that is deemed to be both related and unexpected (i.e. a SUSAR) will be notified to the appropriate Competent Authorities and Research Ethics Committee within 7 days of becoming aware of the event for fatal or life threatening events and 15 days for all other serious events. An SAE will be treated as related if either the PI, CI or both consider it to be related.

Please refer to PROSPER instruction manual for sites for reporting instructions.

12.4 Development Safety Update Report

A developmental safety update report will be submitted to the appropriate Competent Authorities and Research Ethics Committee, once a year for the duration of the trial. The time frame for the report starts with the date of first authorisation by a competent authority in an EU member state and the report should be submitted within 60 days of the anniversary of first authorisation.

12.5 Pregnancies

For female patients, pregnancy should be reported to PHS within 24 hours of becoming aware by completing the pregnancy case report form on the electronic data capture system. In this event, the patient should be withdrawn from the study and replaced. An email should also be sent to [contact] to notify PHS that a pregnancy has occurred.

The pregnancy should be followed up to determine outcome, including spontaneous or voluntary abortion, details of birth and presence or absence of any birth defects, congenital abnormalities or maternal or newborn complications. Any birth defects or congenital abnormalities must be reported as SAEs.

13 UNBLINDING

In Stage 2, the decision to unblind a single case should be made when knowledge of an individual's allocated treatment is required:

- to enable treatment of severe adverse event/s, or
- in the event of an overdose
- to enable reporting of a SUSAR
- patient request (patient would be removed from the trial should this request be granted)

13.1 Unblinding during working hours approval and responsible person

Requests for unblinding of individuals should be made via the Prossper team based in Scottish Clinical Trials Research Unit (SCTRU). Agreement of the Chief Investigator (CI) or a delegate will then be sought. However, in circumstances where there is insufficient time to make this request or for agreement to be sought, the treating clinician should make the decision to unblind immediately. The unblinding procedure can be completed by the SCTRUC Quality Assurance (QA) Team.

13.2 Unblinding during out of hours approval and responsible person

During out of hours, and should it not be possible to contact the CI or delegate, the treating clinician should make the decision to unblind immediately if it will influence the patient's immediate management. All instances of unblinding should be recorded and reported in writing to SCTRUC Prossper team by the local investigator.

The unblinding procedure can be completed by the local investigator or the on-call pharmacist at the site where the patient was randomised. .

13.3 Unblinding for data safety reporting approval and responsible person

Requests for unblinding of individuals should be made via the Prossper team based in SCTRUC. Agreement of the CI or delegate will then be sought. The unblinding procedure can be completed by the SCTRUC QA Team. The Principal Investigator will assess every Serious Adverse Event (SAE) reported against the Investigational Medicinal Product (IMP) as will CI and if this results in a Suspected Unexpected Serious Adverse Reaction (SUSAR) assessment then unblinding will be performed.

13.4 Unblinding procedure and documentation

Unblinding will be done via the Interactive Voice Technology (IVR). This is a telephone or web-based application.

All instances of unblinding should be recorded and reported in writing to SCTRUC Prossper team by the local investigator, including the identity of all recipients of the unblinding information.

Details of how a patient can be unblinded will be included in the site file and in the patient's medical records. This will also be covered in the site initiation visit.

Allocation should not routinely be revealed to Prossper personnel, the CI, or members of the research team at the site.

At the end of the study, participants (or their GPs) may request to be unblinded in order to inform ongoing treatment decisions. In such cases, the CI will have a telephone conversation with the participant or GP, to include discussion of the methodological and scientific advantages of maintaining the blind until the data is analysed. If the CI is not available to have this conversation, it will be made by another senior member of the trial team. Following this conversation, if the participant or GP still wishes to be unblinded, a request to SCTRU Prossper team to permit unblinding will be made. If the SCTRU Prossper team agrees, the unblinding will be done by the SCTRU QA Team, such that the CI, trial office team and site research team can remain blind to treatment allocation.

14 DATA MANAGEMENT

All data will be handled, computerised and stored in accordance with the Data Protection legislation and Public Health Scotland Confidentiality Guidelines.

14.3 Data Collection

Data generated will be entered by site staff onto a Trial specific eCRF. SCTRU will be responsible for checking the data, and validating it. All source data should be recorded within patient files.

The data collected will include:

- initial clinical details at randomisation
- drug administration (progesterone/placebo and dexamethasone) including concomitant medications
- adverse events
- blood tests (see Appendices 4 & 5) including endocrine studies
- ongoing clinical details during study period
- patient questionnaires

14.4 Record Keeping and Archiving

PHS will store study documentation until the end of patient follow up. The documentation will then be archived for 5 years after the end of trial notification has been submitted. .

15 STATISTICS

15.3 Sample Size

In the absence of data necessary to make an informed power calculation for the secondary efficacy endpoint, this sample size for this study was arrived at empirically but is supported by clinical experience and/or simulated data, as outlined below.

In a group of 36 patients randomised 1:1 between intervention and control we would have 90% power to demonstrate an effect size of -1.00 between the two groups, and 80% power to demonstrate a difference of -0.85. In the context of the endpoint being final dexamethasone dose on Day 14, scenarios that would result in this effect size or greater are clinically reasonable (see below).

Final Dexamethasone dose	
+ placebo	+ progesterone

Mean	SD	Mean	SD	SD (pooled)	Effect size	N (per arm)	N (total)
4	2	2	2	2	-1.0	18	36
4	1	2	1	1	-2.0	6	12
2	1	1	1	1	-1.0	18	36

To further illustrate the potential effect sizes that we would be able to identify, and to assess the power that $n=36$ would provide for the *cumulative* dose of dexamethasone across the study period, simulated data have been generated, based on assumptions drawn from clinical experience. In these data the mean effect size (1000 simulations) for the final and cumulative dexamethasone doses was -0.88 and -1.04 respectively. The power that we have to detect effect sizes of this magnitude with $n=18$ (per arm) is 83.05% and 92.13% respectively.

A one sided t-test was used to calculate the sample size as we are testing specifically for reduction rather than a difference. The one sided t-test is exploratory and the primary outcome is safety.

15.4 Randomisation and Stratification

After ensuring that the patients meet **all** eligibility criteria and has consented to participate in the study, sites will randomise the patient following the instructions described in the PROSSPER work instructions for sites. Once a patient has been randomised, a patient study number will be issued and this should be used in all correspondence.

Stage 2 of the PROSSPER trial will be randomised into two treatment groups: Progesterone arm or placebo arm. Randomisation will be a 1:1 allocation; 18 patients in each group stratified by clinical site (Leeds and Liverpool).

15.5 Analysis Plan

The final analysis will be performed on the evaluable population (that is, patients who successfully completed the 14-day treatment period and were not subsequently found to be ineligible); no interim analysis is planned. Unless otherwise stated, 80% confidence intervals will be used; 1-sided p-values calculated and $\alpha=0.05$ as a threshold for significance. Substantial missing data (i.e., missing in >10% patients) will be highlighted in statistical study reports but not imputed. A full statistical analysis plan will be developed prior to any analyses being performed.

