2.2.2.2 Secondary

- Compliance with the structured dexamethasone dose reduction guidelines at 75% of decision points in at least 13 of 18 patients in line with protocol guidelines and as clinically appropriate.
- Description of dexamethasone related symptoms and QOL.
- Percentage of patients achieving a $\geq 50\%$ reduction in dexamethasone dose taken on Day 14
- Comparison (progesterone v placebo) of final dexamethasone dose on Day 14

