9.2.2 Stage 2 recruitment is less than anticipated

We have looked at the number of potentially eligible patients and our recruitment plan is conservative. In the event of recruitment slowing we will engage with colleagues, in particular those in the lung cancer and melanoma team; [name] is a senior member of the breast team. In the event of a further “surge” in COVID-19 cases, mandating suspension of recruitment and redeployment of trial staff, we will record all such instances and seek recompense from the NHS or other bodies for whom they are temporarily working. Patients discontinuing for reasons other than progesterone toxicity will be replaced.

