10. WITHDRAWAL OF SUBJECTS

Patients may withdraw from the study at any point, including after giving consent to the trial but before starting treatment; no further data collection will take place.

Patients may discontinue the study for reasons including toxicity, non-compliance, withdrawal of consent or if the investigator judges' continuation not to be in the patient's best interest. Any patient who does not start IMP, will be replaced.

In Stage 1, patients from whom two full pharmacokinetic profiles cannot be obtained will also be replaced

In Stage 2, patients withdrawing due to the toxicity of micronised progesterone will be replaced. The patients replaced will, however, remain evaluable for assessment of tolerability and if such withdrawals occur in >20% of patients the combination of progesterone and dexamethasone will be considered unacceptably toxic.

If at any point throughout the trial, a patient becomes unable to swallow, they should be withdrawn.

Any patients who permanently discontinue IMP should receive the non IMP dexamethasone and other standard of care treatments.

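### The randomised dexamethasone comparisons are limited to patients who complete 14 days of treatment, and the doses of those who stop early may not be recorded

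*Protocol*

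**What the plan says.** Section 15.5 fixes the population for the whole analysis: "The final analysis will be performed on the evaluable population". It defines that population as "patients who successfully completed the 14-day treatment period and were not subsequently found to be ineligible". Missing data are reported but not imputed. The Final analysis subsection that follows (numbered 14.4) lists the between-arm comparisons of final dose, cumulative dose and time to final dose, and names no other population for them. The first is also a listed secondary endpoint in 2.2.2.2: "Comparison (progesterone v placebo) of final dexamethasone dose on Day 14".

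Non-completers are replaced. Section 3.1.6 replaces Stage 2 patients who are not evaluable. Section 9.2.2 says: "Patients discontinuing for reasons other than progesterone toxicity will be replaced". Sections 9.2.3 and 10 also replace patients who withdraw because of progesterone toxicity. Section 10 keeps those patients evaluable, but only for tolerability.

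On data after withdrawal, section 10 opens with patients who choose to withdraw, for whom "no further data collection will take place". Its next paragraph covers discontinuing the study for toxicity, non-compliance, withdrawn consent or investigator judgement. It adds that if "a patient becomes unable to swallow, they should be withdrawn". Section 11.3 adds: "If the second reduced dose is not tolerable, the patient will be withdrawn from the study". Section 10 ends by saying that patients who permanently stop study drug go on to dexamethasone and standard care.

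**The concern.** Completing 14 days is an outcome that occurs after randomisation and can depend on the allocated treatment. If the arms lose different kinds or numbers of patients, the remaining completers are no longer comparable groups. Replacement restores the count to 18 per arm but not the comparability.

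Some routes out of the study could plausibly relate to dexamethasone need: investigator judgement, inability to swallow, and toxicity. Section 1.5.4 associates somnolence, fatigue and dizziness with high-dose progesterone, so unequal withdrawal between arms is possible.

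The comparisons carry weight despite their exploratory label. Section 15.5 gives them one-sided p-values against 0.05. Section 9.1 makes possible efficacy in reducing dexamethasone a success criterion. Section 2 says the comparator arm will help design the definitive trial. If doses after stopping study drug are not collected, no later analysis plan can recover them.

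**Working it through.** **Inputs from the protocol**
- 18 per arm, 1:1 (15.4), reached by replacing non-evaluable patients (3.1.6).
- One-sided t-test (15.3), threshold 0.05 (15.5).
- Final dose on placebo: mean 4 mg, SD 2 mg (first scenario in 15.3).
- Toxicity withdrawal of up to 20% is accepted before the combination is called unacceptably toxic (9.2.3, 10).

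**Assumptions, because the protocol gives no figures**
- Withdrawal rates by arm, w_A (progesterone) and w_P (placebo). The main case is 20% v 5%.
- The correlation ρ between the tendency to withdraw and the Day 14 dose, taken to be the same in both arms.

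**Step 1: the plan's own power.** Noncentral t, df = 34, noncentrality = d × √(18/2) = 3d.

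| Effect size d | 3d | Stated power | Recomputed |
|---|---|---|---|
| 1.00 | 3.00 | 90% | 90.2% |
| 0.85 | 2.55 | 80% | 80.3% |
| 0.88 | 2.64 | 83.05% | 82.7% |
| 1.04 | 3.12 | 92.13% | 92.1% |

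The figures reproduce, allowing for rounding of the effect sizes. They describe 18 randomised patients per arm and make no allowance for selection.

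**Step 2: bias among completers with no drug effect.** Let a patient withdraw when a standard normal score, correlated ρ with dose, exceeds z(1−w). The completer mean then shifts by −SD × ρ × φ(z)/(1−w), where φ is the normal density.
- w = 0.20: φ/(1−w) = 0.280/0.80 = 0.350.
- w = 0.05: φ/(1−w) = 0.103/0.95 = 0.109.
- Difference between arms at 20% v 5%: −2 × ρ × (0.350 − 0.109) ≈ −0.48ρ mg.

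**Step 3: error rate.** Simulation with 20,000 replicates: withdrawals replaced until each arm has 18 completers, then the one-sided t-test.

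| Withdrawal, progesterone v placebo | ρ = 0 | ρ = 0.3 | ρ = 0.5 | ρ = 1 (extreme) |
|---|---|---|---|---|
| 20% v 5%: bias, mg | 0 | −0.15 | −0.24 | −0.48 |
| 20% v 5%: error rate | 5% | 8% | 10% | 21% |
| 20% v 0%: bias, mg | 0 | −0.22 | −0.35 | −0.70 |
| 20% v 0%: error rate | 5% | 9% | 13% | 31% |
| 10% v 10% or 20% v 20%: error rate | 5% | 5% | 5% | 5% |
| 5% v 20%: bias, mg | 0 | +0.15 | +0.25 | +0.48 |
| 5% v 20%: error rate | 5% | 3% | 2% | 1% |

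Simulated biases agree with the formula in Step 2 within simulation error.

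**Step 4: with a true effect of −2 mg.** At 20% v 5%, the completer estimate is −2.00, −2.14, −2.24 and −2.48 mg for ρ = 0, 0.3, 0.5 and 1. At 5% v 20% it is −2.00, −1.86, −1.76 and −1.52 mg.

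**Step 5: after the change.** With 18 per arm all followed to Day 14, the error rate is 5% and power at d = 1.0 is 90.2%. That is before any dilution from stopping study drug. For comparison, if withdrawals were neither replaced nor followed, losses of 10%, 20% and 28% would leave about 16, 14 and 13 per arm. Power at d = 1.0 would then be 86.8%, 82.4% and 79.7%.

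**The case against.** The strongest reply is that nothing confirmatory rests on these comparisons. Section 2 says no statistical comparison of dexamethasone dosing is planned and calls the work exploratory. Section 11.8 rules out a formal efficacy comparison, and 15.3 says the primary outcome is safety. No decision rule uses the p-value. This stands, and it lowers the priority. It does not remove the selection from results that will be reported with p-values and used in later planning.

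A reader might infer that the patients lost are those with the worst dexamethasone outcomes. The protocol does not support that. Under 11.2 and Appendix 7, recurrent symptoms lead to a dexamethasone increase, not to withdrawal. A patient who is re-escalated, or never comes down from 8 mg, stays in the analysis if the 14 days of treatment are completed. Neurological deterioration is not a listed reason for stopping and could enter only through investigator judgement or inability to swallow. Intolerance leads to two dose reductions before withdrawal (11.3).

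A reader might also infer that all follow-up stops. The sentence ending data collection is attached to patients who choose to withdraw, and adverse events are recorded to 30 days after the last study drug (12.2, 12.3). For patients who only stop study drug the text is ambiguous: section 10 treats them separately, while 11.3 withdraws some of them from the study.

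Finally, 15.5 promises a full analysis plan. Handling of deaths and missing doses can reasonably wait for it. The population cannot be treated as open, because the protocol itself fixes it.

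**Conclusion.** The point holds in a limited form. It is certain from the text that the final analysis, including the randomised dexamethasone comparisons, is restricted to completers and that the others are replaced. Whether dexamethasone doses are recorded after study drug stops is unclear.

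The direction and size of bias are unknown. At an assumed 20% v 5% withdrawal and no drug effect, bias runs from 0 to −0.48 mg and the nominal 5% error from 5% to about 21%, with about 8 to 10% at correlations of 0.3 to 0.5. These figures rest on assumed rates and correlations. Equal rates, with the same mechanism in both arms, give no bias under the null, and the opposite pattern works against progesterone. It would therefore go too far to say that the plan manufactures a steroid-sparing effect. It would also go too far to say that the observed effect will size the next trial: section 2 says only that the comparator arm will aid its design.

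Because the comparison is exploratory, this is something that should be fixed rather than a critical defect. Confidence is high on the wording and low on the size of any bias.

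**What to change.** 1. In 15.5, define the analysis set for all dexamethasone comparisons as every randomised patient who took at least one dose of study drug, analysed by allocated arm, with replaced patients retained. Report the completer analysis as a sensitivity analysis.
2. In section 10, distinguish stopping study drug from withdrawing consent, and reconcile this with 11.3. State that the daily dexamethasone dose is recorded to Day 14 after study drug stops, where consent allows.
3. Use the actual recorded dose wherever there is one. Handling of death or a truly missing Day 14 dose can be set in the analysis plan, for example with worst category as a sensitivity analysis.

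The cost is a wording amendment and a few extra chart entries. The change requires no larger sample. The estimated effect may be smaller, because patients who stopped study drug are included.
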